# 11.10. Pharmacodynamic Analysis

The primary PD endpoint of the study is the change in CI measured by RHC from Baseline to end of infusion at 6 hours. The primary PD analysis will be analyzed be MMRM method. The MMRM model will include treatment group, timepoint, interaction of treatment-by-timepoint, and randomization stratification factor as factors, and Baseline CI as a covariate. An unstructured covariance matrix will be specified for the MMRM model. LS means at visit and LS mean differences between treatment group with p-values and corresponding 95% confidence intervals will be reported.

Potential relationships may be explored between select subject/disease characteristics (eg, Baseline LVEF, Baseline CI, Baseline SBP, duration of HFrEF, renal function, concomitant medications) and select PD measures (eg, change in CI).

Details regarding the statistical analyses will be provided in the SAP.

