## Statistical analyses:

The primary and secondary endpoints will be analyzed using the Full Analysis Set (FAS) and safety endpoints will be performed using the Safety Set. Other important statistical considerations, such as handling missing data imputation strategies, will be described in the SAP.

The primary PD endpoint of the study is the change in CI measured by RHC from Baseline to end IV infusion at 6 hours. The primary PD analysis will be analyzed using a mixed effects model with repeated measures (MMRM) method. The MMRM model will include treatment group, timepoint, interaction of treatment-by-timepoint, and randomization stratification factors as factors, and Baseline CI as a covariate. An unstructured covariance matrix will be specified for the MMRM model. LS means at visit and LS mean differences between treatment group with p-values and corresponding 95% confidence intervals will be reported.

Continuous variables measured at scheduled timepoints will be analyzed using MMRM method. The MMRM model will include treatment group, timepoint, interaction of treatment-by-timepoint, and randomization stratification factor as factors, and Baseline measure as a covariate. An unstructured covariance matrix will be specified for the MMRM model. LS means at visit and LS mean differences between treatment group with p-values and corresponding 95% confidence intervals will be reported.

Unless otherwise specified, continuous endpoints will be analyzed using analysis of covariance (ANCOVA) with a model that includes treatment group and randomization stratification factors as factors and Baseline CI value and other Baseline values as covariates. LS means, Ses, and 95% confidence intervals for the treatments and their difference will be presented together with their p-values.

Where statistical assumptions (eg, normality, proportional odds) are not met, alternative approaches will be evaluated (eg, non-parametric analysis, log transformation).

Details regarding the statistical analyses will be provided in the SAP.

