# **3.1. Overall Design**

This is a Phase 2, multicenter, randomized, double-blind, placebo-controlled, single-dose study assessing the hemodynamic effects, safety, tolerability, and PK of APD418 in subjects with HFrEF to be conducted in 2 parts (Part A and Part B). Each part consists of a Screening Period (up to 21 days in Part A and up to 14 days in Part B), a single dose of randomized study treatment (APD418 or placebo) as a 6-hour IV infusion on Day 1 (Dosing Period) followed by an 18- to 24-hour in-clinic observation period (Postdose Period), and a Follow-Up phone call 7 days (± 2 days) after discharge (Figure 1). Subjects participating in Part A cannot participate in Part B.

On Day 1, potential eligible subjects (per initial Screening criteria) will undergo additional eligibility assessments during the Predose Period on Day 1. Hemodynamic eligibility criteria based on right heart catheterization (RHC) will be assessed at Baseline for final confirmation of eligibility and randomization. Hemodynamic parameters based on RHC will be assessed at the end of Baseline (after at least 2-hour stabilization period), during the Dosing Period throughout the study treatment administration (6-hour IV infusion), and for an additional 1 hour after cessation of study treatment administration. Subjects will continue to be observed during the Postdose Period for a minimum of 18 hours after the end of study treatment administration for PD, PK, and safety assessments prior to discharge on Day 2. Subjects will be contacted by phone call for follow-up 7 days ( $\pm 2$  days) after discharge.

This study has an adaptive design, in which dose escalation in Part A will inform dose expansion in Part B. Part A is a single-ascending dose (SAD) study planned to consist of 5 cohorts. In each cohort, subjects will be randomized to APD418:placebo in a 5:2 ratio. Randomization will be stratified by Screening LVEF (> 25%,  $\leq 25\%$ ). Following completion of all planned cohorts in Part A, 2 APD418 doses studied in Part A will be selected for expansion in Part B. Part B is a parallel-treatment group study planned to consist of a placebo group and 2 APD418 treatment groups by randomizing additional subjects in 1:1:1 ratio (15 subjects are planned in the placebo group and each APD418 treatment group; Figure 1). Randomization will be stratified by Screening LVEF (> 25%,  $\leq 25\%$ ) and baseline carvedilol use (yes, no).

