# 11. PLANNED STATISTICAL METHODS

## **11.1. General Considerations**

Details regarding the statistical analyses will be provided in the Statistical Analysis Plan (SAP), which will be finalized prior to database lock and unblinding.

Continuous variables will be summarized using the number of observations, mean, standard deviation (SD), median, minimum, and maximum. Categorical variables will be summarized using frequency counts and percentages.

Continuous variables measured at scheduled timepoints will be analyzed using a mixed-effects model with repeated measures (MMRM) method. The MMRM model will include treatment group, timepoint, interaction of treatment-by-timepoint, and randomization stratification factors as factors, and Baseline measure as a covariate. An unstructured covariance matrix will be specified for the MMRM model. Least square (LS) means at visit and LS mean differences between treatment group with p-values and corresponding 95% confidence intervals will be reported.

Unless otherwise specified, continuous endpoints will be analyzed using analysis of covariance (ANCOVA) with a model that includes treatment group and randomization stratification factors as factors, and Baseline CI value and other Baseline value as covariates. The LS means, standard errors (SE), and 95% confidence intervals for the treatments and their difference will be presented together with their p-values.

Categorical endpoints will be analyzed by either the Cochran-Mantel-Haenszel method, Fisher's exact test, or by logistic regression with a model that includes treatment group and randomization stratification factors as factors, and Baseline CI value and other and Baseline value as covariates. The odds ratio relative to placebo and percentage of difference from placebo will be presented together with corresponding 95% confidence intervals and the p-value.

Where statistical assumptions (eg, normality, proportional odds) are not met, alternative approaches will be evaluated (eg, non-parametric analysis, log transformation).

Efficacy data will be analyzed by randomized treatment, while safety data will be analyzed by actual treatment.

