# **11.2.** Determination of Sample Size

Approximately 80 subjects are planned to be enrolled in this study (35 in Part A and 45 in Part B). It is assumed that CI, as measured with RHC, from Baseline to end of infusion is normally distributed with a mean of 2.0 and SD of 0.5. Sixty-five evaluable subjects (20 subjects in each of the 2 APD418 treatment groups and 25 in placebo) is sufficient to achieve at least 80% power to detect a treatment effect of 0.45 in favor of APD418 (a clinically significant improvement of 22.5% from placebo) between each of the APD418 treatment groups and placebo by a 2-sample t-test using a 2-sided significance level of 0.05.

The primary endpoint analysis will be based on pooled data from subjects in Part A and Part B. There will be 2 APD418 treatment groups of 20 subjects each (planned to consist of 5 subjects from Part A and 15 subjects from Part B) and one placebo treatment group of 25 subjects (planned to consist of 10 subjects from Part A and 15 subjects from Part B).

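### The primary model pools two separately randomised Parts with no Part term, so as planned 15% of any residual Part difference enters each dose-placebo contrast unless strata are coded within Part

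*Combined protocol and SAP*

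**What the plan says.** Section 11.2 states the pooling: "The primary endpoint analysis will be based on pooled data from subjects in Part A and Part B". It describes each APD418 group as "planned to consist of 5 subjects from Part A and 15 subjects from Part B" and placebo as "planned to consist of 10 subjects from Part A and 15 subjects from Part B". Section 3.1 gives two separate randomisations. For Part A, "In each cohort, subjects will be randomized to APD418:placebo in a 5:2 ratio"; Part B is formed "by randomizing additional subjects in 1:1:1 ratio".

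Three passages give the model terms. Section 11.10 has "The MMRM model will include treatment group, timepoint, interaction of treatment-by-timepoint, and randomization stratification factor as factors, and Baseline CI as a covariate". The synopsis (Statistical analyses) has "The MMRM model will include treatment group, timepoint, interaction of treatment-by-timepoint, and randomization stratification factors as factors, and Baseline CI as a covariate". Section 11.1, for continuous variables in general, has "The MMRM model will include treatment group, timepoint, interaction of treatment-by-timepoint, and randomization stratification factors as factors, and Baseline measure as a covariate". None lists Part, cohort or period.

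Section 11.3 makes Screening LVEF a stratum in both Parts and baseline carvedilol use a stratum in Part B only. The documents do not say how carvedilol is coded for Part A subjects in the pooled model. Detail is left to the SAP, which the biometrics Note to File addendum of 13 January 2023 reports as a draft (v0.4).

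**The concern.** Placebo subjects come from every Part A cohort, while each expanded dose draws on one cohort. Placebo therefore holds a larger share of Part A subjects than either dose group, by design and not by chance. If CI change differs between Parts for any reason other than treatment, a pooled comparison that ignores Part mixes that difference into the treatment effect. The drug effect is inflated if Part B runs higher and masked if it runs lower.

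The stratification factors might or might not prevent this. If strata are coded within Part (two levels in A, four in B), a constant Part difference is absorbed. If LVEF and carvedilol enter as main effects, it is not. The model statements allow either reading.

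**Working it through.** **Inputs.** Group sizes, SD 0.5, effect 0.45 and two-sided 0.05 are from Section 11.2. Every Part difference below is an assumption. Write D for the Part B minus Part A mean CI change, in L/min/m2, under the same treatment.

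**The plan's own figure.** SE = 0.5 × √(1/25 + 1/20) = 0.1500. The noncentral t with 62 df gives 84.0% power (83.5% with 43 df), so the claim of at least 80% is reproduced.

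**Share of D entering each contrast.** This is the Part A fraction of placebo minus that of the dose group.
- 5 cohorts, as planned: 10/25 − 5/20 = 40.0% − 25.0% = 15.0%
- 4 cohorts: 8/23 − 5/20 = 9.8%
- 6 cohorts: 12/27 − 5/20 = 19.4%

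Section 11.9 permits one cohort more or fewer. A least-squares check with Baseline CI, LVEF and carvedilol as main effects gave 0.099, 0.151 and 0.194 for 4, 5 and 6 cohorts. It gave zero with a Part term or with strata coded within Part.

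These shares hold only if all else is as planned. Section 11.9 also lets Part B be resized: 19 per group gives 19/24 − 19/29 = 13.6%. Section 6.4 allows extra subjects in a cohort, and Cohort 2 reached 15. If such a cohort (assumed split 11:4) were an expanded dose, its share would be 15/26 − 15/27 = 2.1% and the other dose's 15/20 − 15/27 = 19.4%.

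**Size with the planned numbers and no Part term (simulated).**

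| Assumed size of D | Bias = 0.15 × D | % of 0.45 | Null tails (D positive) | Power for 0.45 if D is negative |
|---|---|---|---|---|
| 0 | 0 | 0 | 2.5% / 2.5% | 84.0% |
| 0.1 | 0.015 | 3% | 3.1% / 1.9% | 81.2% |
| 0.2 | 0.030 | 7% | 3.6% / 1.4% | 77.7% |
| 0.3 | 0.045 | 10% | 4.1% / 1.0% | 73.2% |

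Two-sided error stays near 5% because the omitted difference also enlarges the residual variance. The within-group sum of squares for Part is 25 × 0.4 × 0.6 + 2 × 20 × 0.25 × 0.75 = 13.5, so the expected residual variance is 0.25 + D² × 13.5/62. Power stays at or above 80% down to about D = −0.13.

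**Cost of a Part term in precision.** Contrast variance = 0.25 × (1/20 + 1/25 + 0.15²/13.5) = 0.0229, so SE = 0.1514. With 61 df, power is 83.3%, and it stays at about 83% whatever D is.

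**Cost of a Part term through dose selection.** Section 11.9 picks the two doses on unblinded Part A pharmacodynamic data, and the same subjects are then pooled. Consider a chance gain shared by both chosen doses in Part A.
- Without Part its weight in each contrast is 5/20 = 25%.
- With Part, the Part A comparison of 10 dosed with 10 placebo has weight 10 × 10/20 = 5. The Part B comparison of 30 with 15 has weight 30 × 15/45 = 10. The gain enters at 5/15 = 33%.

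As a worst case, take five equal doses with the top two chosen on mean CI change (n = 5 each, SD 0.5). Simulated bias rises from 0.046 without Part to 0.062 with it, and the upper tail from 4.4% to 5.3%.

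**Part B alone.** SE = 0.5 × √(2/15) = 0.183. With 42 df the 95% confidence interval half-width is 0.37 and power is 67%.

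**The case against.** The strongest objection is that the documents give no reason to expect a Part difference. Eligibility, right heart catheterisation method and assessment schedule are shared, and every cohort has blinded randomised placebo. The stated differences are the screening window (21 against 14 days), the allocation ratio and the strata. This stands, and it is why the point is conditional and modest.

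A second objection is that the Part term is not free of bias. Selection on Part A data is built into the design, whereas D is assumed. In the worst case the term adds about 0.015 of bias, which equals what it removes at D = 0.1. This also stands. It weakens the case for Part as a complete remedy and strengthens the case for a Part B-only estimate.

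A third is that the SAP may have coded strata within Part or added the term. The draft is not among the documents, so this cannot be settled. It is the reason for the condition on coding.

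Three stronger readings are tempting and not supported:
- A reader might infer that two-sided error is inflated to 5.5% or 6.0% at D = 0.2 or 0.3. Those figures hold the SE at 0.15 and ignore the larger residual variance.
- A reader might take 9.8% to 19.4% as bounds. They vary the cohort count alone.
- A reader might infer that the reported results are biased. The Note to File shows outputs for Part A Cohorts 1 and 2 only, so there were no Part B data to pool.

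**Conclusion.** The concern holds for the plan as written. The listed model omits a factor by which subjects were separately randomised and which is unbalanced across the groups compared. With the planned numbers the leak is exactly 15% of any constant residual Part difference, unless strata are coded within Part. The harm depends wholly on that difference, which the documents do not give. At 0.1 to 0.3 the bias is 0.1 to 0.3 of a standard error, and the power margin is lost only if Part B is lower by more than about 0.13. The power and error figures assume SD 0.5, complete data and a single-timepoint linear model. This is worth closing before the design is reused; it is not a serious defect.

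**What to change.** - In the synopsis and Sections 11.1 and 11.10, add Part (A/B) and Part-by-timepoint to the MMRM models, and add Part to the ANCOVA. The interaction matters because the endpoint is hour 6. For a difference that builds linearly over the infusion, a Part main effect alone leaves about half the bias (0.037 of 0.075 when the difference reaches 0.5).
- State how carvedilol use is coded for Part A subjects. Yes/no for everyone is feasible, since Section 6.8 requires medications to be recorded for all subjects.
- Prespecify a Part B-only estimate with its confidence interval, reported beside the pooled result. Its main purpose is to give an estimate free of the Part A selection gain. It also answers a limit of the Part term, which removes a step between Parts but not drift between Part A cohorts. Under an assumed linear drift, the term reduced bias in 12 to 16 of 20 dose contrasts and enlarged it in the other 8 to 4. With 67% power the estimate is supportive only.

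The cost is edits to the model statements and one extra analysis, with no new data. If the Parts do not differ, power falls from 84.0% to 83.3%. The plan should also acknowledge the heavier weight on any selection gain (33% against 25%).

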# 11.11. Pharmacokinetic Analyses

PK parameters will be calculated using noncompartmental modeling.

Calculated plasma PK parameters will include, but will not necessarily be limited to AUC0-6, AUClast, AUC0-∞, Cmax,  $t_{1/2}$ ,  $t_{1/2\alpha}$ ,  $t_{max}$ , CL, Vdz, VdSS, MRTlast, and Cave. Urinary PK parameters will include, but not be limited to, the amount of unchanged drug excreted during each collection interval from  $t_1$  to  $t_2$  (Aet1-t2), total amount of unchanged excreted in urine over the collection period (amount excreted [Ae]), renal clearance (CLr) and the fraction of drug excreted unchanged in the urine, expressed as a percentage of total dose (fraction excreted [Fe]).

Collected plasma and urine PK samples may also be used for profiling of drug binding proteins, bioanalytical method validation purposes, stability assessments, or to assess other actions of APD418 with plasma constituents.

A detailed description of all PK analyses will be provided in the SAP.

Potential relationships may be explored between select plasma APD418 exposure parameters and select PD measures (eg, change in CI).

OATP genotyping will be analyzed and presented in the listing to allow any potential future analysis.

## **11.12.** Safety Analyses

AEs will be listed and summarized by system organ class and preferred term, as well as according to severity and causality/relationship to study treatment. TEAEs will be summarized by cohort and treatment group. In addition, TEAEs will be pooled across treatment groups (ie, placebo, APD418). Observed values for clinical laboratory tests, vital signs, and safety 12-lead and ECGs will be summarized by cohort and treatment group. Individual data listings of clinical laboratory tests results will be presented for each subject. Observed values and changes from Baseline will be summarized descriptively. Safety 12-lead ECG data (observed values and change from Baseline) will be listed for each subject and timepoint. Observed values will be classified for normal, abnormality that is not clinically significant, and clinically significant abnormality by cohort, treatment, and timepoint of collection. Results of other safety assessments will be listed and summarized as appropriate.

A detailed description of all safety analyses will be provided in the SAP.

## 11.12.1. Adverse Events

AEs will be coded using the Medical Dictionary for Regulatory Activities (MedDRA).

For each treatment group, the proportion of subjects with TEAEs will be summarized overall, by severity, and by relationship to study treatment. SAEs will also be summarized by treatment group. A TEAE is defined as:

- An AE that occurs after initiation of study treatment that was not present at the time of treatment start.
- An AE that increases in severity after the initiation of medication, if the event was present at the time of treatment start.

AEs occurring before the first dose of study treatment will be summarized separately.

## 11.12.2. Extent of Exposure

The duration of time on study and time on study treatment will be summarized for each treatment group using descriptive statistics.

## 11.12.3. Clinical Laboratory Parameters

Laboratory parameters will be summarized by treatment group at each scheduled assessment timepoint using descriptive statistics.

## 11.12.4. Electrocardiograms

Individual ECG values will be listed by cohort, treatment, and timepoint, and summarized using descriptive statistics. Intervals to be provided for each ECG are RR, PR, QRS, QT, QTc, QTcB, and QTcF. Post-Baseline ECGs for each subject will be compared with the Baseline ECG. Any clinically significant change from Baseline may be recorded as an AE if deemed appropriate by the Investigator, or Investigator in consultation with the Clinical Lead. Outlier analysis will be performed on all subjects with QTcF values greater than 500 ms or change from Baseline > 60 ms in the absence of Baseline ECG abnormalities that preclude accurate surface ECG assessment of ventricular repolarization (eg, bundle branch block).

## 11.12.5. Vital Signs

Descriptive statistics for vital signs (SBP, DBP, HR, respirations, and body temperature) will be presented by treatment group.

#### 11.12.6. Physical Examination

Clinically significant physical examination abnormalities will be included in medical history or recorded and summarized as an AE.

# **12.** ETHICAL CONSIDERATIONS

## **12.1.** Ethical Conduct of the Study

This study shall be conducted in accordance with the ethical principles that have their origin in the Declaration of Helsinki and that are consistent with GCP, ICH guidelines, and other applicable regulatory requirements (eg, local requirements).

# 12.2. Institutional Review Board or Independent Ethics Committee Approval

Before initiating a study, the Investigator must have written and dated approval from the IRB/IEC for the study protocol, written ICF, subject recruitment materials and procedures (eg, advertisements or websites), and any other written information to be provided to subjects. Approval from the committee must be documented in a letter to the Investigator specifying the protocol number, protocol version, documents reviewed, and the date on which the committee met and granted the approval.

All documents subject to review during the study, including any modifications made to the protocol after receipt of IRB/IEC approval, must also be submitted to the committee for approval prior to implementation. The Investigator must also provide periodic reports as required and promptly report important safety information (ie, SAEs) and protocol violations, as appropriate, to the IRB/IEC.

As part of the Investigator's written application to the IRB/IEC, the Investigator should provide the committee with a current copy of the IB. If the IB is updated during the study, the Investigator should supply an updated copy to the committee.

# 12.3. Informed Consent

The Investigator will fully inform the subject of all pertinent aspects of the study, including the approval of the study by the IRB/IEC. Before informed consent may be obtained, the Investigator should provide the subject ample time and opportunity to inquire about details of the study and to decide whether to participate.

Prior to a subject's participation in the study, the IRB/IEC-approved ICF must be signed and personally dated by the subject and by the person who conducted the informed consent discussion. If a subject is unable to read, an impartial witness will be present during the entire informed consent discussion.

The written ICF and any other written information to be provided to subjects should be revised whenever important new information becomes available that may be relevant to the subject's consent. Any revised written ICF or study materials to be available and/or supplied to subjects should receive the IRB/IEC's approval in advance of use. The subject will be informed in a timely manner if new information becomes available that may be relevant to the subject's willingness to continue participation in the study. The communication of this information should be documented.

